24 HOUR CONTACT TELEPHONE #: [REDACTED]

The Medical Monitor should be notified by the clinical site in writing and by telephone within 24 hours of learning of a Serious Adverse Event. The Medical Monitor may be contacted during business hours for adverse event questions. General study related questions should be directed towards your assigned clinical research associate.

The Medical Monitor should be notified by the clinical site in writing and by telephone within 24 hours of learning of a Serious Adverse Event (SAE).

Detailed Instructions for Review of Adverse Events

Notes:

1. Refer to Sections 8.1 through 8.5 of the study protocol for safety parameters and adverse event definitions.
2. The CTMS adverse event reports are entitled Serious Adverse Events, but the reports include all Adverse Events.

Review THIS section...	AE Forms (initial report and follow-up) ...And cross-check with THESE	Look for or consider
AE Description and AE Diagnosis	
• Onset• Severity• Outcome• AE Category• Copies of relevant information provided by site (e.g., hospital reports, labs, etc.)	
• Medically consistent/logical?
Relationship to Test Article (AE Categories: not related, doubtful, possible, probable and very likely)	
• Onset• Study Agent(s) and Dosing	
• Medically logical/possible?
Outcome (resolved, ongoing, not resolved, resolved sequelae, fatal, resolving & unknown)	
• AE Description• AE Category• Study Agent(s) and Dosing• Copies of relevant information provided by site (e.g., hospital reports, labs, etc.)	
• Medically consistent/logical?
AE Category	
• AE Description• AE Diagnosis• Outcome• Copies of relevant information provided by site (e.g., hospital reports, labs, etc.)	
• Medically consistent/logical?

1.6 ESTIMATED REPORT DATE

Approximately 60 days post data hard lock.

1.7 CHANGE HISTORY

Version	Originator	Document Change History	
		Description of Change(s)	Date
1.0	[name]	New Protocol	08 December 2016
2.0	[name]	PRO version 3.0 (Section 16.1)	09 January 2017
3.0	[name]	Protocol date updated	18 January 2017
4.0	[name]	
Section 3.1: Old Text “when worn for 30 (-2/±6) days on daily wear modality” replaced by “when worn for approximately 30 days”.Section 4.7.1, Treatment 1, Assignment 1 updated from “rules” to “guide” and the instruction to “choose the least minus sphere” was removed.[REDACTED] added to the appendix.	14 March 2017

1.8 PROTOCOL SYNOPSIS

Protocol Number and Title: CR-5871 Evaluation of Astigmatic Contact Lenses
Sponsor: JJVC, [name]
Investigational Product: senofilcon C toric contact lenses and Air Optix for Astigmatism
Regimen and Dosing: Subjects will be assigned to wear one of two study lenses bilaterally for approximately 30 days in a daily wear, monthly replacement modality.
Phase or Type of Study: Design validation study
Study Objectives: To demonstrate that the senofilcon C toric in its final lens design meets the design validation requirements related to corneal staining, lens fitting characteristics, visual acuity and rotational performance of senofilcon C toric contact lenses as well as subjective comfort and handling.
Other Endpoints/Observations: 
Subjective CLUE visionGSI QuestionnaireLens deposits
Study Design: This is a randomized, double-masked, bilateral dispensing parallel group design study. Subjects will be assigned to wear one of two study lenses bilaterally for approximately 30 days in a daily wear, monthly replacement modality.
Sample Size: Approximately 270 eligible subjects will be enrolled and a minimum of 230 are targeted to complete the study (115 subjects per arm). A replacement subject may be enrolled if a subject discontinues from the study prematurely. The decision to enroll replacement subjects will be made by the joint agreement of the Investigator and Sponsor.

Eligibility Criteria:

Subjects must meet all study Inclusion Criteria as outlined below:

- 1) Healthy adult males or females age \geq 18-40 years of age with signed informed consent.
- 2) The subject must appear able and willing to adhere to the instructions set forth in this clinical protocol.
- 3) Subject must be a habitual soft toric contact lens wearer. Habitual wearer is defined as someone who wears contact lenses for at least 6 hours a day, 5 days a week for the past 30 days.
- 4) Subject's vertex corrected spherical component of their distance refraction must be between -1.00 to -4.75D (inclusive) in each eye.
- 5) Subject's vertex corrected refractive cylinder must be between -0.75 and -1.50DC (inclusive) in each eye.
- 6) Subject's refractive cylinder axis must be 180 ± 25 and 90 ± 15 in each eye.
- 7) The subject must have visual acuity best correctable to 20/25 or better for each eye
- 8) The subject must read and sign the Informed Consent form.

Subjects meeting any of the following Exclusion Criteria will not be eligible to participate in the study:

- 1) Women who are pregnant or breastfeeding
- 2) Any ocular or systemic allergies or diseases that may contraindicate contact lens wear.
- 3) Any ocular medications use within the last one month.
- 4) Any systemic disease, autoimmune disease, or use of medication, which may interfere with contact lens wear.
- 5) Any infectious disease (e.g., hepatitis, tuberculosis) or a contagious immunosuppressive disease (e.g., HIV), by self-report.
- 6) Habitual wearer of extended wear contact lenses.
- 7) Known sensitivity to Revitalens OcuTec®
- 8) Any previous history of ocular and/or refractive surgery (e.g., radial keratotomy, PRK, LASIK, etc.).
- 9) A clinical finding or history of entropion, ectropion, extrusions, chalazia, recurrent styes, glaucoma, history of recurrent corneal erosions, aphakia, or moderate or above corneal distortion, by self-report.
- 10) History of binocular vision abnormality or strabismus, by self-report.
- 11) Habitual wearer of rigid gas permeable (RGP) lenses, orthokeratology lenses, or hybrid lenses (e.g. SynergEyes, SoftPerm) within the past 6 months.
- 12) Employee of investigational clinic (e.g., Investigator, Coordinator, Technician).
- 13) Participation in any contact lens or lens care product clinical trial within 14 days prior to study enrollment.
- 14) Clinically significant (grade 3 or higher) corneal edema, corneal vascularization, corneal staining, tarsal abnormalities, bulbar injection or any other abnormalities which would contraindicate contact lens wear.
- 15) Any history of a contact lens-related corneal inflammatory event within the past year that may contraindicate contact lens wear.
- 16) Any active ocular infection.
- 17) Any corneal distortion resulting from previous hard or rigid gas permeable contact lens wear.
- 18) Any fluctuations in vision due to clinically significant dry eye or other ocular conditions.

Disallowed Medications: Use of any prescription or over-the-counter (OTC) medications that may affect contact lens wear from 24 hours prior to receiving the study product throughout study participation.

2.1 NAME AND DESCRIPTION OF INVESTIGATIONAL PRODUCTS

The following contact lenses will be used in this study:

LENSES		
Test Article Form	Test	Control
Design / Description	senofilcon C toric	Air Optix for Astigmatism
Lot Number or Other Identifier e.g., Compass Protocol Number or Lens ID Code	[REDACTED] [REDACTED]	[REDACTED] [REDACTED] [REDACTED]
Manufacturer	JJVC	Alcon
Packaging Form	Blister	Blister
Nominal Distance Powers (D)	-1.00 to -4.50 in 0.25 steps	-1.00 to -4.50 in 0.25 steps
Nominal Cylinder Powers (D)	-0.75, -1.25	-0.75, -1.25
Nominal Base Curve @ 22 oC	8.5/14.5	8.7/14.5
Material	senofilcon C	lotrafilcon B
Cylinder Axis (°)	80, 90, 100, 10, 20, 160, 170, 180	80, 90, 100, 10, 20, 160, 170, 180
Overall Diameter (mm)	14.5	14.5

The following solutions will be used in this study:

SOLUTIONS	
Solution Name / Description	Revitalens OcuTec®Multi-Purpose Disinfecting Solution
Manufacturer	Abbott Medical Optics

2.2 SUMMARY OF FINDINGS FROM NONCLINICAL STUDIES

2.3 SUMMARY OF KNOWN RISKS AND BENEFITS TO HUMAN SUBJECTS

See [REDACTED]

2.4 DESCRIPTION OF TRIAL TREATMENTS

The test lens is senofilcon C formulated using the same monomeric components for currently marketed senofilcon A, in different ratios. The control lens is Alcon Air Optix® for Astigmatism which is currently marketed as a monthly replacement. The study lenses will be worn in a bilateral and random fashion using a parallel group design. Using a computer-generated randomization scheme, each subject will randomly be assigned to one of two lenses in a 1:1 ratio. The test and control lenses will be worn as daily wear for approximately thirty days.

2.5 STATEMENT OF COMPLIANCE TO PROTOCOL, GCP, AND APPLICABLE REGULATORY GUIDELINES

This trial will be conducted in compliance with the protocol, the International Conference on Harmonization Good Clinical Practice E6 (ICH-GCP), the Declaration of Helsinki, and all applicable regulatory requirements.

2.6 DESCRIPTION OF POPULATION TO BE STUDIED, ENROLLMENT TARGETS, AND STUDY DURATION

Approximately 270 eligible subjects will be enrolled and a minimum of 230 are targeted to complete the study (115 subjects per arm). Subjects will be ≥ 18 and ≤ 40 years of age. Enrolled subjects must be habitual wearers of soft toric contact lenses in both eyes.

Approximately 50% of study subjects will be habitual monthly replacement modality toric wearers including Air Optix for Astigmatism and Biofinity Toric. Habitual is defined as at least one month of lens wear where the lenses are worn a minimum of six hours per day and a minimum of five days per week. Subject participation is expected to be approximately 30 days.

2.7 RELEVANT LITERATURE REFERENCES AND PRIOR DATA

See [REDACTED]

3.1 DESCRIPTION OF OBJECTIVES AND PURPOSE

The objectives of this study are to evaluate corneal staining, lens fitting characteristics, visual acuity, rotational performance, and the subjective comfort of senofilcon C toric contact lens compared to Air Optix for Astigmatism when worn for approximately 30 days.

The following will be monitored and evaluated:

1. Adverse events
2. Lens fit characteristics
3. Vision characteristics
4. Physiological characteristics
5. Ocular symptoms
6. Lens deposits
7. Average wear time
8. Reasons for discontinuation
9. Lens damage

4.1 PRIMARY AND SECONDARY ENDPOINTS

The primary endpoints for this study are:

- Monocular distance visual acuity 20/40 or better,
- Contact lens related corneal staining,
- Lens fitting acceptability,
- Absolute rotation
- Stability with blink.

Monocular visual acuity (VA) will be assessed with the study lenses using a Snellen distance VA chart at an optical distance of 20 feet throughout the study. Observed monocular VA collected during planned visits will be dichotomized whether VA was ‘20/40 or better’ or ‘worse’. VA of 20/40 with a negative modifier will be considered to be worse than 20/40. Additionally, observed monocular VA will be dichotomized whether VA was ‘20/20 or better’ or ‘worse’ at fitting using the same logic as the previous VA category.

Contact lens related corneal staining will be assessed via slit lamp throughout the study. Corneal staining will be graded using a 5-level scale; 0=no staining, 1=trace, 2=mild, 3=moderate and 4=severe. Observed corneal staining collected during planned and unscheduled visits will be dichotomized whether the corneal staining is ‘grade 2 or lower’ or ‘Grade 3 or higher’.

Lens fit characteristics will be assessed via slit lamp in terms of lens position, movement and tightness. Each lens fit collected at fitting will be judged as being either ‘acceptable’ or ‘unacceptable’ based on the static and dynamic fit characteristic.

Lens rotation will be assessed via slit lamp with beam that can be rotated. The rotational error (assume shortest distance) and direction (base towards the nose or based towards temple) will be calculated. Absolute rotation will be dichotomized whether rotation was ‘> 10-degree’ or ‘worse’ upon 15 minute post insertion at fitting.

Rotational stability with blink will be assessed via slit lamp with beam that can be rotated. The stability of the scribe mark rotational position during a series of normal (unforced) blinks will be observed. Observed rotational stability with blink will be dichotomized whether stability was ‘> 5-degree’ or ‘worse’ at fitting.

The secondary endpoints are:

- Monocular distance visual acuity 20/20 or better,
- Subjective CLUE comfort score, and
- Subjective CLUE handling score

Subjective CLUE comfort and handling score will be assessed using the Contact Lens User ExperienceTM (CLUE) questionnaire. CLUE is a validated patient-reported outcomes (PRO) questionnaire to assess patient-experience attributes of soft contact lenses (comfort, vision, handling, and packaging) in a contact-lens wearing population in the US, ages 18-65. Derived CLUE scores using Item Response Theory (IRT) follow a normal distribution with a population average score of 60 (SD 20), where higher scores indicate a more favorable/positive response. A 5 point increase in an average CLUE score translates into 10% shift in the distribution of scores for population of soft disposable contact lens wearers.

The following primary and secondary hypotheses will be tested throughout the study using a gate keeping strategy. The secondary hypotheses will be tested only if all primary hypotheses are met. Otherwise, no secondary hypotheses testing will be performed.

Primary Study Hypotheses	
1	At least 80% of eyes in the Test group will have monocular visual acuity of 20/40 or better throughout the wear period.
2	The incidence rate of observing contact lens related corneal staining grade 3 or higher for the Test lens will be no different or better than that of the Control lens throughout the wear period.
3	At least 80% of lens fits in the Test group will have acceptable fit at fitting.
4	At least 80% of lens fits in the Test group will have absolute rotation \leq 10 degrees upon 15 minutes post insertion at fitting..
5	At least 80% of lens fits in the Test group will have rotational stability with blink \leq 5 degrees at fitting.
Secondary Study Hypotheses	
1	The proportion of eyes with visual acuity 20/20 or better in the Test group will be non-inferior to that of the Control group at fitting (a non-inferiority margin of 10% will be used).
2	The overall CLUE comfort score assessed throughout the study for the Test lens will be non-inferior to that of the Control lens. A non-inferiority margin of -5 will be used.
3	The overall CLUE handling score assessed throughout the study for the Test lens will be superior to 50 CLUE handling score.

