6.3 UNSCHEDULED VISITS

If, during the investigation, a subject experiences any investigational device-related difficulties and/or problems requiring an unscheduled visit to the clinic, the following information will be collected at a minimum:

- Chief complaint prompting the visit. If the reason is an adverse event, the applicable eCRF for the adverse event should be completed and source documentation completed as appropriate.
- Date and time of the visit and all procedures completed at the unscheduled visit
- Review of adverse event and concomitant medications
- Documentation of any investigational product dispensed or collected from the subject.
- Slit lamp findings (using the Slit Lamp Classification Scale)

If the Investigator withdraws a subject from the study, the final study visit case report forms must be completed indicating the reason(s) why the subject was withdrawn. The subject enrollment log should be completed documenting the date and primary reason for withdrawal and the study CRA notified.

Any investigational device-related difficulties and/or problems that are ongoing at the time of the final study visit will be followed by the Investigator, within licensure, until they have returned to pre-treatment status, stabilized, or been satisfactorily explained. If further treatment (i.e., beyond licensure) is required, the subject will be referred to the appropriate health care provider.

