9.1 STATISTICAL METHODS TO BE EMPLOYED

All data summaries and statistical analyses will be performed using the SAS software Version 9.4 or above (SAS Institute, Cary, NC). Throughout the analysis of data, the results for each subject/eye will be used when available for summarization and statistical analysis. Unscheduled visits will be summarized separately and excluded from the statistical analysis.

Summary tables (descriptive statistics and/or frequency tables) will be provided for all baseline, efficacy and safety variables as appropriate. Continuous variables will be summarized with descriptive statistics including n, mean, standard deviation (SD), median, minimum and maximum. Categorical variables will be summarized using frequency count and percentage of subjects or eyes within each category. Summaries will be presented by study lens type and will be performed separately by study population defined in section 9.7.

Safety variables will be summarized descriptively for the safety population. The primary analyses will be conducted on the safety population and the secondary analyses will be conducted on the per protocol population due to nature of the study endpoints (refer to section 9.7). If the dropout rate is higher than 20%, a sensitivity analysis will be conducted for the efficacy endpoints on all randomized subjects who successfully tried at least one study lens.

Monocular Visual Acuity (VA) 20/40 or better Analysis:

Each eye/subject will be categorized into two groups such that 'response=1' if an eye had acceptable VA (i.e., VA 20/40 or better) throughout all planned visits or 'response=0' otherwise. The generalized mixed model will be used to assess the overall acceptable VA for each lens type separately utilizing binomial distribution with logit link function. The model will include lens type as a fixed effect and site, subject and eye nested within subject as random effects. Baseline characteristics such as age and gender may be also included in the model as covariates if appropriate.

The model based proportion of eyes with acceptable VA with its corresponding 95% confidence interval (CI) will be constructed for each lens type from the generalized linear mixed model. Overall acceptable VA will be concluded if the lower limit of the 95% CI is greater than or equal to 0.80 (80%).

Lens Fit Acceptance Analysis:

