1.4. Statistical Hypotheses for Study Objectives

1.4.1. Primary Hypotheses

The co-primary endpoints for this study are:

- Monocular distance visual acuity 20/40 or better,
- Lens fitting acceptability,
- Stability with blink,
- Absolute rotation, and
- Contact lens related corneal staining.

Monocular Visual Acuity (VA) 20/40 or better

The proportion of dichotomized monocular VA 20/40 or better in the Atlas A group will be compared to a historical control proportion (p_0) of 80%. The alternative hypothesis (denoted as H_a) is at least 80% of eyes in the Atlas A group will have monocular visual acuity 20/40 or better throughout all planned visits (Visits 1 through 5) whereas the null hypothesis (denoted as H_0) is less than 80% of eyes in the Atlas A group will have monocular visual acuity 20/40 or better. The following hypothesis testing for proportion will be assessed:

$$H_0: p < p_0 \text{ vs. } H_a: p \geq p_0,$$

where p represents the population proportion and p_0 represents a historical control proportion of 80%.

Lens Fitting Acceptability

The proportion of acceptable lens fit at fitting (Visit 1) in the Atlas A group will be compared to a historical control proportion (p_0) of 80%. The alternative hypothesis is at least 80% of eyes in the Atlas A group will have acceptable lens fit at fitting whereas the null hypothesis is less than 80% of eyes in the Atlas A group will have acceptable lens fit. The following hypothesis testing for proportion will be assessed:

$$H_0: p < p_0 \text{ vs. } H_a: p \geq p_0,$$

where p represents the population proportion and p_0 represents a historical control proportion of 80%.

Stability with Blink

The proportion of dichotomized adequate lens stability with blink (adequate stability is defined as lens stability with blink \leq 5-degree) at fitting (Visit 1) in the Atlas A group will be compared to a historical control proportion (p_0) of 80%. The alternative hypothesis is at least 80% of eyes in the Atlas A group will have adequate lens stability with blink at fitting whereas the null hypothesis is less than 80% of eyes in the Atlas A group will have adequate lens stability with blink. The following hypothesis testing for proportion will be assessed:

$$H_0: p < p_0 \text{ vs. } H_a: p \geq p_0,$$

where p represents the population proportion and p_0 represents a historical control proportion of 80%.

Absolute Rotation

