5.2.1. Definition

Monocular Visual Acuity (VA) 20/40 or better

Monocular VA with the study lenses will be assessed using a Snellen distance VA chart at an optical distance of 20 feet throughout the study. Observed monocular VA collected during the planned visits (Visits 1 through 5) will be dichotomized whether VA was '20/40 or better' (refer as 'acceptable VA') or 'worse'. VA of 20/40 with a negative modifier will consider to be worse than 20/40. Each eye/subject will be categorized into two groups such that 'response=1' if an eye had acceptable VA or 'response=0' otherwise.

Lens Fit Acceptance

Lens fit characteristics will be assessed via slit lamp in terms of lens position, movement and tightness. Each lens fit collected at fitting (Visit 1) will be judged as being either 'acceptable' or 'unacceptable' based on the static and dynamic fit characteristic.

Lens Stability with Blink

Rotational stability with blink will be assessed via slit lamp with beam that can be rotated. The stability of the scribe mark rotational position during a series of normal (unforced) blinks will be observed. Observed rotational stability with blink will be dichotomized whether stability was ' \leq 5-degree' or 'worse' at fitting (Visit 1).

Absolute Rotation

Lens rotation will be assessed via slit lamp with beam that can be rotated. The rotational error (assume shortest distance) and direction (base towards the nose or based towards temple) will be calculated. Absolute rotation will be dichotomized such that 'response=1' if absolute rotation was less than equal to 10-degree (refer as 'acceptable rotation') or 'response=0' otherwise upon 15-minute post insertion at fitting (Visit 1).

Contact Lens Related Corneal Staining (CS)

Contact lens related corneal staining will be assessed via slit lamp throughout the study. Corneal staining will be graded using a 5-level scale; 0=no staining, 1=trace, 2=mild, 3=moderate and 4=severe. Observed corneal staining collected during planned and unscheduled visits will be dichotomized whether the corneal staining is 'grade 2 or lower' or 'Grade 3 or higher'.

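### The VA 20/40 co-primary is scored on planned visits only, although Protocol hypothesis 1 claims the whole wear period and staining, worded the same way, also counts unscheduled visits

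*Protocol*

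**What the plan says.** **VA 20/40.** Protocol 4.1 states hypothesis 1 as: "At least 80% of eyes in the Test group will have monocular visual acuity of 20/40 or better throughout the wear period". The endpoint definition in that section reads "Observed monocular VA collected during planned visits will be dichotomized". Protocol 9.1 gives response=1 "if an eye had acceptable VA (i.e., VA 20/40 or better) throughout all planned visits", and 0 otherwise. SAP 5.2.1 has the same scope: "Observed monocular VA collected during the planned visits (Visits 1 through 5) will be dichotomized". SAP 5.2.2 agrees, and SAP 1.4.1 states the hypothesis itself for planned Visits 1 to 5.

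**Corneal staining.** Hypothesis 2 in Protocol 4.1 also refers to the whole wear period, but here "Observed corneal staining collected during planned and unscheduled visits will be dichotomized". Protocol 9.1 and SAP 5.2.1 and 5.2.2 follow that rule.

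**Unscheduled visits.** Protocol 6.3 describes them as arising from "investigational device-related difficulties and/or problems requiring an unscheduled visit to the clinic". Its minimum data list includes slit lamp findings but no acuity with the study lens. The opening of Protocol 9.1 keeps unscheduled visits out of the statistical analysis and summarises them separately.

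**Precedence.** SAP 1.1 makes the SAP the final analysis guidance and lets it override Protocol Section 9. It does not name Section 4.1.

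**The concern.** Two co-primary hypotheses share the phrase about the wear period but are scored on different sets of visits, and no reason is given. SAP 1.4.1 indicates what the phrase means: for staining it describes the comparison both as covering all planned and unplanned visits and as covering the wear period. On that reading the VA endpoint does not cover the period that hypothesis 1 claims.

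The direction is fixed. A responder must be acceptable at every counted visit, so adding a visit can turn a success into a failure but never the reverse. Leaving out the unscheduled visits can therefore only help the lens, and those visits are the ones prompted by lens problems. VA 20/40 is tested in the Test arm alone against 80%, so equal leniency in the Control arm offsets nothing.

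At stake is mainly the accuracy of the reported Test proportion for the wear period, and only remotely the pass/fail result.

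**Working it through.** **1. The rules side by side**

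| | VA 20/40 | Staining |
|---|---|---|
| Protocol hypothesis (4.1) | wear period | wear period |
| Protocol endpoint (4.1) | planned visits | planned and unscheduled |
| Protocol analysis (9.1) | planned visits | planned and unscheduled |
| Protocol 9.1 general rule | unscheduled excluded | unscheduled excluded |
| SAP hypothesis (1.4.1) | planned Visits 1–5 | planned and unplanned |
| SAP endpoint and analysis (5.2.1, 5.2.2) | planned visits | planned and unscheduled |

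The SAP is consistent within itself. For VA, the mismatch lies between Protocol hypothesis 1 and every scoring rule. For staining, Protocol 9.1 contradicts its own general rule; SAP 5.2.2 settles that.

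**2. Can a relevant reading exist?** Yes, though none is required. The Protocol 6.3 list is a minimum, and all procedures done at the visit are to be recorded. Protocol 5.1 has discontinued subjects complete a last follow-up form, which may belong to an unscheduled visit, and scheduled follow-up visits include Snellen acuity. The form's content is not shown.

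**3. The plan's own figure.** Protocol 9.2 gives power above 90% at 90 per arm, assuming a 95% rate and a between-eye correlation of 0.8. A simulation of 20,000 trials of paired eyes, with success when the lower 95% limit is at least 0.80, gave 99.4% to 99.98% at 90 per arm. The range spans cluster-robust Wald limits (identity and logit scale) and Agresti-Coull limits. The mixed model was not fitted. The plan's lower bound is reproduced.

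**4. Size per eye.** The primary analysis uses the safety set (SAP 2.3.2 and 5). Taking all 135 planned Test subjects as included:
- Eyes: 135 × 2 = 270.
- One eye: 1/270 = 0.37 points.

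The 115 per arm is the completer target. It gives 230 eyes and 1/230 = 0.43 points, but leaves out the early leavers whom the safety set keeps.

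**5. Assumed range.** The documents give no rate of eyes failing only at unscheduled visits. If 1–5% of Test subjects have one such eye, the overstatement is half that, 0.5–2.5 points; if both eyes, 1–5 points.

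**6. Power if those failures are counted** (logit-Wald, correlation 0.8):

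| Points of eyes failing only there (true rate) | 115 per arm | 135 per arm |
|---|---|---|
| 0 (95%) | >99.9% | about 100% |
| 1 (94%) | 99.8% | 99.9% |
| 2 (93%) | 99.2% | 99.7% |
| 3 (92%) | 97.3% | 98.8% |
| 5 (90%) | 85.9% | 91.6% |

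**7. Distance from the criterion.** Effective n = eyes/(1 + 0.8). The lower limit is expit{logit(p) − 1.96/√[n_eff·p(1−p)]}.
- 270 eyes: n_eff = 150. With 36 failures, p = 0.867 and the limit is just above 0.80; with 37 it falls below. Expected failures at 95%: 0.05 × 270 = 13.5. About 23 further failures are needed to miss (37 − 13.5 = 23.5).
- 230 eyes: n_eff = 127.8. The criterion allows 29 failures against 11.5 expected, so about 18 further failures are needed.

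**The case against.** **The SAP already aligns hypothesis and analysis.** This is true for VA, and a reader who infers that the two documents disagree throughout would be wrong. But SAP 1.1 names only Protocol Section 9 as overridden. Hypothesis 1 sits in Section 4.1 and still claims more than is tested.

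**The asymmetry has a practical basis.** Slit lamp findings are required at unscheduled visits and acuity is not, so staining is ascertained there and acuity need not be. This stands. It limits what the change can capture and means the needed data cannot be assumed to be on the forms. The best-corrected acuity required for adverse events (Protocol 8.4, 8.5) is not acuity with the study lens. None of this justifies ignoring a reading that was taken.

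**A persistent loss would be caught anyway.** For subjects who continue, planned visits follow every 6–9 days, with Snellen acuity taken twice at Visits 2 to 4. What escapes is mainly a loss that resolves before the next planned visit. This also stands, and it keeps the effect small.

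**Stronger readings that the documents do not support:**
- *Every eye seen with poor acuity at an unscheduled visit is scored a success.* This is certain only for eyes acceptable at all planned visits. An eye that also fails a planned visit is a failure. If the subject leaves at the unscheduled visit, later planned visits are missing and the scoring is undefined: the otherwise-0 clause points one way; no imputation and use of results when available point another.
- *Such failures are hidden.* Protocol 9.1 summarises unscheduled visits separately, and adverse events are listed by eye.

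**Conclusion.** The concern holds as a one-sided mismatch in a co-primary endpoint. Protocol hypothesis 1 speaks for the wear period, while the scoring ignores study-lens acuity recorded at the visits most likely to reveal a lens-related loss. Staining, worded alike, does not ignore them.

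The size is about 0.37 points of the Test proportion per affected eye. This assumes about 270 Test eyes in the safety set; the number of affected eyes is unknown, and the 1–5% range is an assumption.

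A reader might infer that the VA conclusion is at risk. The figures do not support that. The planning rate is 95%, the historical rate in Protocol 9.2 is 100% for both lenses, and about 23 extra failing eyes (about 18 with 230 eyes) would be needed to miss the criterion. These counts rest on a correlation of 0.8 and a logit-Wald approximation, not on the planned mixed model. The change is worth making because the bias has a known direction and is cheap to remove.

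**What to change.** 1. In Protocol 4.1 and 9.1 and SAP 1.4.1, 5.2.1 and 5.2.2, define response=1 for VA 20/40 as 20/40 or better at all planned visits and at any unscheduled visit with a study-lens reading. State that a recorded reading worse than 20/40 gives response=0 whether or not later planned visits are missing.
2. Exempt VA 20/40 and staining from the Protocol 9.1 sentence that removes unscheduled visits from the statistical analysis. For staining this brings the protocol into line with the SAP.
3. Add Snellen acuity with the study lens to the minimum data in Protocol 6.3. Without this, item 1 counts only readings that a site happened to take.
4. If the planned-visit rule is kept, narrow Protocol hypothesis 1 to planned visits, as SAP 1.4.1 already does, and report the wider count as a sensitivity analysis.

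The cost is a few phrases and, with item 3, one acuity measurement per unscheduled visit. The reported success rate may be slightly less favourable. On the figures above, the planned sample size need not change: at 135 per arm, power stays above 90% even with 5 points of added failures.
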